7.2.3 Randomization/Pre-Conditioning fMRI Visit (Day 0) – In Person/Remote

Participants will sign their long form written consent at this visit prior to any further study procedures.

Exhaled breath CO (eCO) will be measured at the start of the visit. A urine sample will also be collected and tested for cotinine using the NICCheck cotinine test and pregnancy if participants are of child bearing potential. Eligible participants will then be randomized to one of the four conditions and asked to complete the baseline assessments. This includes the standardized smell test (B-Sit), adverse events assessment and computerized questionnaires of cigarette use, cigarette dependence, liking, and withdrawal as indicated in Table 1. Some of the measures can be done remotely via Zoom, others will need to be completed in person. The remote assessments will be conducted via a Zoom session within 3 days following the scheduled in-Person MRI. The remote visit will only occur after written consent has been obtained. This is being done to limit the amount of face-to-face time during study visits.

Then, participants will complete the fMRI odor cue-reactivity task in the MRI scanner lasting approximately 45 minutes. During the scan, participants will be administered four flavors in separate 4 minutes blocks for eight runs. The flavors will be delivered to the participant's nostrils via tubing from the olfactometer machine. The release of the flavors will be timed with participants' natural rate of respiration and randomized across blocks. At the end of this visit participants will be given the ECIG device and 4-week supply of their randomly assigned flavor cartridges (approximately 2 cartridges/day) and instructed on how to use the device.

Participants will be instructed to take at least 50 puffs per day from the ECIG device to replace conventional cigarette smoking. The participant will be instructed to bring back all used and unused cartomizers to the study center. ECIG puffs per day and cigarettes per day will be recorded on a daily log. Participants will receive a daily REDCap survey link via text message using the Twilio service. Participants will be instructed on how to complete the survey and will be provided with a paper log to tally their cigarette use throughout the day. Participants who are unable or unwilling to receive study text messages will track their cigarette use on the paper log only.

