7.4 Test Article(s) (Study Drug(s) and/or Study Device(s))

7.4.1 Description

The ECIG used will be the EGO ECIG. Previous work has shown that the EGO ECIG was capable of delivering nicotine to its users.²⁶ This ECIG is made up of 2 parts, a battery and a cartomizer. The cartomizer contains the heating element and the liquid. The liquid used in the cartomizer will contain either 0 mg/ml or 18 mg/ml of nicotine and be either tobacco or strawberry vanilla

flavor. The nicotine concentration in the liquid and the flavor will be determined by random assignment. The cartomizers will be filled with liquid by the researchers and will be used once by the participant and returned to researchers.

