7.4.2 Treatment Regimen

Participants will be randomized to one of four conditions:

- Tobacco flavor ECIG (18 mg/ml nicotine concentration)
- Tobacco flavor ECIG (0mg/ml nicotine concentration)
- Strawberry Vanilla flavor ECIG (18 mg/ml nicotine concentration)
- Strawberry Vanilla flavor ECIG (0mg/ml nicotine concentration)

Participants will be instructed to use their ECIG for at least 50 puffs per day to replace conventional cigarette use.

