7.4.3 Method for Assigning Subject to Treatment Groups

Blocked randomization stratified across gender and matched for age will be accomplished with a 1:1:1:1 ratio of condition assignments with a goal of 56 randomized over a 7 month recruitment period. The randomization list will be stored in a password protected document that will only be accessed by unblinded study personnel.

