8.2 Sample size determination

For the proposed between-subject analyses, we will be looking for trends in the hypothesized direction, not statistical significance with traditional parametric statistics. With an estimated medium effect size, we will have approximately 50% power to find a liberal between-subject effect ($p<.10$) for the proposed t-test between the flavor groups on baseline cue-reactivity, 60% power to detect changes in cue-reactivity between the nicotine content and flavor groups, and 90% power to detect within-subject changes in cue-reactivity at $p<.05$. Groups will be stratified by gender to estimate gender effects for future research.

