Aim 2: Examine the effect of flavor and nicotine on ECIG odor cue-reactivity after conditioning. Two-sample t-test will be conducted in FSL for the strawberry vanilla>rose and tobacco>rose odor difference score z- statistic images comparing the 18 mg to 0mg nicotine content ECIG groups. A paired two-sample t-test will be conducted to compare the tobacco>rose and strawberry vanilla>rose odor difference score z-statistic image separately for each 18 mg/ml ECIG flavor group. These t-tests will identify anatomical regions with significant effects of nicotine level and assigned vs. unassigned flavor over time. We expect that BOLD activity in regions implicated in smoking cue-reactivity will increase more over the conditioning phase for the 18 mg nicotine group compared to the 0mg nicotine group and for odors from the assigned vs. unassigned flavor.

Aim 3: Determine if strawberry vanilla results in stronger cue-reactivity than tobacco flavor. A two-sample t-test will be conducted for the assigned flavor (strawberry vanilla or tobacco) > control rose difference score z- statistic images comparing the flavor groups. These t-tests will identify anatomical regions with significant flavor group (tobacco vs. strawberry vanilla) by time (baseline to post-randomization) interaction effects on each odor image. For this analysis, only the 18 mg/ml nicotine content flavor groups will be included.

Exploratory Behavioral Aim: Determine if changes in flavor cue-reactivity are associated with changes in ECIG satisfaction, liking, craving, and dependence. One-sample t-tests will assess for anatomical regions where BOLD changes in odor cue-reactivity are correlated with changes in behavioral measures of e- cig satisfaction, craving, and dependence collected at the 2-week check-in and post-randomization visit, and changes in ECIG liking collected at the baseline and post-randomization visits.

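### Aim 2's nicotine test ignores which flavor each participant was assigned, so it dilutes the conditioning effect by a factor that depends on how far conditioning generalizes across odors

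*Combined protocol and SAP*

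**What the plan says.** The trial is a 2x2 design, flavor by nicotine. Section 7.4.1 states: "The nicotine concentration in the liquid and the flavor will be determined by random assignment". Section 7.4.3 sets a "1:1:1:1 ratio of condition assignments with a goal of 56 randomized", and section 7.2.3 gives each participant a "4-week supply of their randomly assigned flavor cartridges". Within the trial, each person is therefore conditioned on one e-liquid odor.

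In section 8.3, Aim 2 has two parts:

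- **Nicotine:** a two-sample t-test on the strawberry vanilla>rose and the tobacco>rose change images, described as "odor difference score z- statistic images comparing the 18 mg to 0mg nicotine content ECIG groups". Assigned flavor is not mentioned.
- **Assigned vs unassigned odor:** a paired test run within each 18 mg/ml flavor arm.

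The stated expectation is a larger rise in the 18 mg group "compared to the 0mg nicotine group and for odors from the assigned vs. unassigned flavor". Aim 3 uses the contrast matched to assignment: "A two-sample t-test will be conducted for the assigned flavor (strawberry vanilla or tobacco) > control rose difference score". Section 8.2 gives "60% power to detect changes in cue-reactivity between the nicotine content and flavor groups", based on a medium effect size with no number attached.

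**The concern.** Each nicotine test mixes two kinds of participant. For the strawberry vanilla odor, half of each nicotine group used strawberry vanilla study liquid for four weeks and half used tobacco. The tobacco odor is the mirror image. Only the first half had the tested odor paired, or deliberately not paired, with nicotine by the study product. The plan expects the response to the unassigned odor to rise less, and uses that odor as the comparator in its paired test. It then averages the two kinds of participant when it looks for nicotine.

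No other planned test compares 18 mg with 0 mg. The paired tests and Aim 3 are confined to the 18 mg arms. A null or weak nicotine result could therefore reflect the choice of odor rather than the absence of a conditioning effect. The estimate carried into later work would also be smaller than the effect on the conditioned odor.

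**Working it through.** **Inputs from the documents**

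- 56 randomized 1:1:1:1 (7.4.3), so 56/4 = 14 per arm. Each nicotine group has 28 participants, 14 per flavor.
- Threshold p<.10 for between-subject effects, and 60% power for the nicotine and flavor group comparisons (8.2).

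**Assumptions not in the documents**

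- d = 0.5 for a medium effect on the assigned odor.
- Two-sided testing.
- SD of 1 within each arm.
- No dropout.
- One outcome per test, with no image-wise correction.

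**Step 1. Reproduce the stated power.** For a two-sample t-test with n per group, the noncentrality is d x sqrt(n/2) on 2n-2 degrees of freedom. With n = 28 and d = 0.5 it is 0.5 x sqrt(14) = 1.87 on 54 df, with critical value 1.67. Power is 58% (59% by the normal approximation), close to the stated 60%. With 14 vs 14, power is 36%. The stated figure thus fits a full medium effect in whole nicotine groups, with no allowance for dilution.

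**Step 2. Effect in the test as written.** Let g be the 18 mg minus 0 mg effect on the unassigned odor, as a fraction of the effect on the assigned odor. Half of each group has the tested odor as its assigned odor, so

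tested effect = (d + g x d)/2 = d x (1+g)/2.

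Mixing the two halves adds (d(1-g))²/4 to the variance in the 18 mg group. At g = 0 that is 0.0625. The average variance is (1.0625 + 1)/2 = 1.031, the SD is 1.016, and the standardized effect is 0.25/1.016 = 0.246.

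**Step 3. Power by g** (28 vs 28, two-sided .10, noncentral t, mixture variance included)

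| g | Tested effect | Power |
|---|---|---|
| 0 | 0.25 | 24% |
| 0.25 | 0.31 | 31% |
| 0.5 | 0.375 | 40% |
| 0.75 | 0.44 | 49% |
| 1 | 0.50 | 58% |

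**Step 4. Alternatives.**

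- Each participant's assigned odor>rose change, 28 vs 28, keeps d = 0.5 and gives 58%. Fitting flavor and the flavor-by-nicotine term (52 df) also gives 58%.
- Restricting each odor to its own flavor arms removes the dilution but leaves 14 vs 14, with 36% power.

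**Step 5. Two odor tests, two chances.** A simulation at g = 0 with d = 0.5 gives at least one uncorrected result at p<.10 in about 41% of trials if a person's two odor changes are uncorrelated, and 36% if they correlate at 0.5. Both are below 58%. With no effect at all, the chance of at least one such result is about 19% when they are uncorrelated.

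**The case against.** **Pooling is inferred.** Section 8.3 does not say that the flavor arms are combined, so a matched reading, with each odor tested only in its own flavor arms, is possible. It is the less natural one, because the same section states its restrictions where it wants them (the paired test and Aim 3). The 60% figure cannot settle this. It is quoted for the flavor comparison too, which under Aim 3 is 14 vs 14. It also cannot separate a pooled per-odor test from an assigned-odor test, since both are 28 vs 28.

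**A reader might infer that the effect is halved and power is 24%.** That is the g = 0 case only. The plan predicts a larger rise for the assigned odor, not an absent one elsewhere. The size is therefore a range, and this part of the objection stands.

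**A reader might infer that half of each group had never vaped the tested odor.** Section 3.1 admits daily e-cigarette users, and Aim 1 anticipates users of both tobacco and fruit flavors. The statement holds only for the study product during the trial. Smokers may also go on smoking (7.4.4). Neither exposure is the randomized pairing under test, so the dilution argument survives.

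**The power figures are soft.** Section 8.2 seeks trends in a predicted direction, which may mean one-sided testing. At one-sided .10 (without the small mixture-variance term) the figures are 72% at g = 1, 54% at g = 0.5 and 36% at g = 0. The FSL analysis searches for regions, so single-outcome power is only indicative. The factor (1+g)/2 depends on neither choice.

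**The pooled test is not invalid.** Flavor is balanced by randomization, so it estimates without bias an average nicotine effect on each odor. This stands: the problem is sensitivity and relevance to the hypothesis, not bias.

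**Conclusion.** The point holds as a dilution of uncertain size. Read plainly, Aim 2's nicotine test includes 14 of 28 participants per group whose study flavor was not the odor being tested, and the plan's own expectation of assigned above unassigned implies g below 1. The tested effect is then (1+g)/2 of the assigned-odor effect. Power lies between 24% (g = 0) and 58% (g = 1), with 31% to 40% for g between 0.25 and 0.5, against a stated 60%. These figures rest on d = 0.5, two-sided p<.10, equal SDs, no dropout and a single-outcome test.

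The documents do not support treating this as a fatal flaw. The study is a proof of concept that looks for trends, and the pooled comparison is less sensitive rather than wrong. It is a worthwhile correction because it concerns the only planned comparison of 18 mg with 0 mg.

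**What to change.** In section 8.3, make the main Aim 2 nicotine comparison each participant's assigned odor>rose change, 18 mg vs 0 mg (28 vs 28), with assigned flavor in the model. This is the contrast Aim 3 already uses. Report the same comparison on the unassigned odor>rose change as a specificity check, and report odor-specific nicotine effects through the flavor-by-nicotine term. State which arms enter each test, and state the effect size and sidedness behind the figure in section 8.2.

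The cost is a change of wording and some re-analysis of scans already planned, with no new participants or visits. It does not clearly reduce the number of tests, since the plan does not rank them and the specificity check and interaction are reported as well. There are two real downsides. Odor-specific nicotine effects become secondary. The assigned-odor test also averages over flavors whose nicotine effects may differ: section 1.1 expects a larger rise with 18 mg/ml strawberry vanilla than with 18 mg/ml tobacco, and the 58% assumes the same nicotine effect in both flavors. A lighter option keeps the two per-odor tests and adds assigned flavor and its interaction with nicotine. The undiluted effect for each odor then rests on 14 vs 14, with about 36% power.

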1.0 Objectives

1.1 Study Objectives

The current proposal aims to establish proof-of-concept that neural cue-reactivity can serve as an early, objective marker of electronic cigarette (ECIG) addictive potential. Further, this proposal will examine the effect of flavor and nicotine concentration on the addictive potential of ECIGs to aid research informing U.S. Food and Drug Administration (FDA) flavor regulations and smoking cessation.

The specific aims of the study are:

Aim 1: Determine if smokers and e-cigarette users have pre-conditioned neural cue-reactivity to tobacco or fruit-flavored ECIG odors.

Aim 2: Examine the effect of flavor and nicotine on ECIG odor cue-reactivity after conditioning.

Aim 3: Determine if strawberry vanilla flavor results in stronger cue-reactivity than tobacco flavor.

Hypothesis: We expect the group assigned to the 18 mg/ml strawberry vanilla flavor to show larger increases in neural cue-reactivity to their assigned odor than the 18 mg/ml tobacco flavor group.

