7.2.5 Post-Conditioning fMRI Visit (Day 28 ± 7 days) – In Person/Remote

Participants will attend a final visit to complete biomeasures, computerized surveys, the adverse events assessment, and the same fMRI tasks as the baseline MRI visit as indicated in Table 1. Some of the measures can be done remotely via Zoom, others will need to be completed in person. The remote assessments will be conducted via a Zoom session ± 3 days of the scheduled in-Person MRI. This is being done to limit the amount of face-to-face time during study visits. eCO will be measured and urine will be collected for cotinine and pregnancy tests. At the end of the visit, participants will be debriefed and counseled on smoking cessation. All participants will be given a copy of the Surgeon General's booklet 'How Tobacco Smoke Causes Disease' (SEE ATTACHMENT: Surgeon General's Booklet).

Table 1: Measures Table (Black X – In Person; Green X – Remote)

	Final Screening	Randomization/ Pre-Conditioning fMRI	Check-In	Post- Randomization fMRI
Visit	1	2	3	4
Day	-7	0	14	28
QUESTIONNAIRES				
Visit Screener	X			
Tobacco Use History	X			
Name Registry	X			
MRI Safety Form	X	X		X
Demographics	X			
Medical History	X			
Concomitant Medications	X	X	X	X
Adverse Event Assessment		X	X	X
Cigarette Details	X			
CCQ (Clinical COPD Questionnaire)	X	X	X	x
Alcohol Audit-C	X			
NIDA Quick Screen	X			
Environmental Smoke Questionnaire	X			
MINI Psychiatric Interview	X			
Daily Smoking and ECIG Use Logs	X (cigarette only)	X	X	X
Cigarette Dependence (Fagerstrom and Penn State Cigarette Dependence Index)		X	X	X
Minnesota Withdrawal Scale		X	X	X
Craving		X	X	X
Cigarette liking scale		X	X	X
ECIG Use History	X	X	X	X
ECIG evaluation scale			X	X
ECIG Side Effects			X	X
ECIG dependence			X	X
ECIG Perceived Health Risk			X	X
ECIP Patterns of Use			X	X
Perceived Benefits and Harms of Using ECIG		X		X
PROCEDURES				
B-SIT Smell Test		X		
fMRI Cue-Reactivity Task in Scanner		X		X
BIOMEASURES				
Pregnancy Test		X		X
Exhaled CO		X		X
Urine Sample Collection		X		X
NICCHECK Rapid Cotinine Test		X		X

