7.2.10 Flavor-Cue Reactivity Details

The olfactometer (ETT, inc: <http://www.emergingtechtrans.com>) will be used to deliver the e-liquid odors to the nose during a respiration-triggered event-related fMRI cue-reactivity task. The tobacco and strawberry vanilla e-liquid flavors, as well as two common control scents, Lavender and PEA (phenyl ethyl alcohol; that smells like rose), will be delivered in randomized order during 4-minute blocks over 8 runs. The flavors will be delivered for 4 seconds every 20-30 seconds depending on respiration rate. At the end of the task, participants will be delivered each odor again and asked to rate how much they like the flavor using a fiber-optic button box.

The lavender odor is an experimental control condition that encourages participants to maintain attention and task engagement during the MRI scan. It provides us with a quality control manipulation, whereby if we suspect from poor data quality that a participant was not paying attention in the scanner, we can confirm this if they were also not responding to the lavender scent as instructed.

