8.3 Statistical methods

Images collected during the fMRI odor cue reactivity task will be preprocessed using a standard Functional Magnetic Resonance Imaging of the Brain Software Library (FSL) software pipeline. Blood oxygen level dependent (BOLD) activation during the tobacco, strawberry vanilla, and rose flavors will be modeled using a double-gamma hemodynamic response function, contrasted to one another, and merged across the two runs for each participant. To create images that capture changes from baseline to post-conditioning, a difference z- statistic image will be calculated by subtracting the baseline image from the post-conditioning image. The lavender odor is an experimental control condition that encourages participants to maintain attention and task engagement during the MRI scan. It is not part of the endpoints of the study.

Aim 1: Determine if smokers and ECIG users have pre-conditioned neural cue-reactivity to tobacco or strawberry-vanilla ECIG odors. One- sample t-test will be conducted on the contrast of tobacco > strawberry vanilla, tobacco > rose, strawberry vanilla > rose to identify anatomical brain regions where tobacco elicits greater neural activation over strawberry vanilla and rose odors and strawberry vanilla elicits greater activation over rose odors. We expect tobacco odor to elicit greater activation in the ventral striatum, amygdala, anterior insula, and OFC than the strawberry vanilla and rose for combustible cigarette smokers and tobacco-flavored e-cigarette users. We expect strawberry-vanilla odor to elicit greater activation in ventral striatum, amygdala, anterior insula, and OFC than tobacco and rose for fruit-flavored e-cigarette users.

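### Aim 3 compares change in two different odors between the 18 mg/ml arms, so any odor-specific scan-to-scan change enters the flavor estimate; the same-odor contrasts should be added

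*Combined protocol and SAP*

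**What the plan says.** Section 1.1 states the Aim 3 hypothesis: the 18 mg/ml strawberry vanilla group is expected to show "larger increases in neural cue-reactivity to their assigned odor than the 18 mg/ml tobacco flavor group".

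Section 8.3 turns this into a two-sample t-test "for the assigned flavor (strawberry vanilla or tobacco) > control rose difference score" images, comparing the flavor groups. The difference score is the post-conditioning image minus the baseline image. The sentence that follows says the tests will find regions with "flavor group (tobacco vs. strawberry vanilla) by time (baseline to post-randomization) interaction effects on each odor image". The analysis set is restricted: "only the 18 mg/ml nicotine content flavor groups will be included".

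Two other sections show which data exist. Section 7.2.10 delivers "The tobacco and strawberry vanilla e-liquid flavors, as well as two common control scents, Lavender and PEA" in the task, so every participant smells both e-liquid odors and rose. Section 7.2.5 repeats "the same fMRI tasks as the baseline MRI visit" at follow-up. Both odor-versus-rose change images are therefore available in both arms, and Aim 2 already uses them.

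**The concern.** The strawberry vanilla arm enters the test with its response to one odor, and the tobacco arm with its response to another. Randomization makes the people in the two arms comparable; it does not make the two odors comparable. Subtracting rose removes only change that all odors share. If strawberry vanilla and tobacco responses change by different amounts between scans for reasons unrelated to the assigned product, that difference appears as a flavor effect.

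The plan itself makes unequal change plausible. Aim 1 expects tobacco odor to produce "greater activation in the ventral striatum, amygdala, anterior insula, and OFC" in cigarette smokers and tobacco-flavor users before any study product is used, and expects the same of strawberry vanilla odor in fruit-flavor users. The two odors may therefore habituate differently. Participants are also told to use the study product in place of cigarettes (section 7.4.2), while section 7.4.4 expects them to go on smoking. Either could shift tobacco-odor reactivity in both arms, whatever flavor was assigned.

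The two Aim 3 sentences also do not clearly define one analysis. The first puts a different odor in each arm. The second, with "by time (baseline to post-randomization) interaction effects on each odor image", reads most naturally as both arms compared on the same odor, once per odor.

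Aim 3 carries the one hypothesis set out in section 1.1, and the study is meant to inform flavor regulation (section 2.3).

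**Working it through.** **Inputs.**
- 56 randomized 1:1:1:1 (section 7.4.3), so 14 per arm. Aim 3 uses 14 v 14, before any dropout or scan loss.
- The level p<.10 is taken from section 8.2, which does not state sidedness. It attaches p<.10 to the baseline flavor-group test; applying it to Aim 3 is an assumption.
- A medium effect is taken as d = 0.5 (assumed; section 8.2 gives no number).
- Odor drift has no source in the documents. A range of 0.1 to 0.5 SD of the change score is assumed.

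**The plan's own figure.** Section 8.2 states 60% power for changes between the nicotine and flavor groups. With 28 v 28, d = 0.5 and two-sided p<.10, power is 58.9% (normal) or 58.0% (noncentral t), so 60% is reproduced for 28 v 28. At Aim 3's 14 v 14 the same test has 36.2% power (noncentral t).

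**What each contrast estimates.** Let c_S and c_T be the conditioning effects of assignment on the strawberry vanilla and tobacco odors. Let g_S and g_T be the change in each odor-versus-rose response that would occur anyway, and let D = g_S − g_T.
- Strawberry vanilla arm: S change = c_S + g_S; T change = g_T.
- Tobacco arm: S change = g_S; T change = c_T + g_T.
- Assigned-odor test: (c_S + g_S) − (c_T + g_T) = (c_S − c_T) + D.
- Same odor, S: (c_S + g_S) − g_S = c_S.
- Same odor, T (tobacco arm minus strawberry vanilla arm): (c_T + g_T) − g_T = c_T.
- Difference of the two same-odor contrasts: c_S − c_T, free of D.

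A baseline difference between odors does not appear in these expressions, because it cancels in post minus baseline.

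**Rejection by the assigned-odor test when c_S = c_T.** Noncentral t with 26 df and noncentrality D√(14/2). For D = 0.3 this is 0.3 × 2.646 = 0.794, against a two-sided critical value of 1.706.

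| D (SD, assumed) | Two-sided p<.10 | One-sided, drift favors strawberry vanilla | One-sided, drift favors tobacco |
|---|---|---|---|
| 0 | 10.0% | 10.0% | 10.0% |
| 0.1 | 11.1% | 15.4% | 6.2% |
| 0.2 | 14.5% | 22.3% | 3.6% |
| 0.3 | 19.9% | 30.8% | 2.0% |
| 0.5 | 36.2% | 50.8% | 0.5% |

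**Simulation** (40,000 replicates, 14 per arm, two-sided p<.10, odor-change correlation r of 0, 0.5 and 0.8). With D = 0.5 and no conditioning, the assigned-odor test shows a mean effect of about 0.50 SD and rejects about 36%. The same-odor tests and their difference stay at about 10%. With D = −0.5 and a true strawberry vanilla advantage of 0.5 SD, the assigned-odor estimate is about 0 and rejection is about 10%. Drift can therefore hide an effect as well as create one.

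**Price of the drift-free contrast.** The difference of the two same-odor contrasts equals the arm comparison of (S change + T change). Its variance relative to the assigned-odor test is 2(1 + r): 2, 3 and 3.6 at r = 0, 0.5 and 0.8. For a 0.5 SD advantage the standardized effect is 0.5/√[2(1 + r)] = 0.354, 0.289 and 0.264. Power at two-sided p<.10 is 23.7%, 19.2% and 17.7%, against 36.2% for the assigned-odor test with no drift.

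**The case against.** The strongest defense is that the assigned-odor test is the one that matches the hypothesis in section 1.1, and that nothing in the documents shows the two odors drifting unequally. Both points stand. They are reasons to keep the test and to treat the drift sizes as a sensitivity range. They do not remove D from the estimate.

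The rates above are also for a single outcome. Aim 3 is an image-wide search for regions, and section 8.2 says the between-subject analyses look for trends. The rates show how sensitive the test is to drift; they are not the error rate of the planned imaging procedure.

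The second sentence can be read otherwise. A between-group test of change scores is a group-by-time interaction, and the phrase about each odor image could mean each arm's assigned-odor image. If it does mean one test per odor, the same-odor tests are already planned. The text has to say which.

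A reader might infer more than the documents support:
- *That different baseline reactivity by itself biases the test.* It does not; it cancels in the change score. Only unequal change matters.
- *That a positive result could never be separated from drift.* Aim 2 plans paired tests of tobacco against strawberry vanilla change within each 18 mg/ml arm. Their strawberry-vanilla-minus-tobacco expectations are c_S + D and D − c_T, so drift alone predicts the same shift in both arms. This is some information, but weak at 14 per arm, and each test carries D itself.
- *That the assigned-odor test should give way to the same-odor tests.* A single same-odor test keeps 36% power but asks only whether assignment conditions that odor. The contrast that addresses stronger conditioning costs power. It also assumes that using one flavor does not change the response to the other odor, and it doubles any general arm effect common to both odors.

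**Conclusion.** The concern holds in this form: the Aim 3 test as worded estimates the difference in conditioning plus D, and neither the rose control nor randomization removes D. The algebra depends on no assumed size.

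The consequence does. For an assumed D of 0.1, 0.2, 0.3 or 0.5 SD, 14 per arm and no conditioning difference, two-sided rejection at p<.10 is 11%, 14.5%, 20% and 36%. One-sided it is 15%, 22%, 31% and 51% if drift favors strawberry vanilla, and below 10% if it favors tobacco. Neither the size nor the direction of drift is known from the documents.

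For a proof-of-concept study this is a matter of adding contrasts, tempering the claim and clearing up the wording. It does not invalidate the aim. The two sentences need to be reconciled in any case.

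**What to change.** 1. Reconcile the two Aim 3 sentences in section 8.3, naming for each test the odor image and the arms compared.
2. Keep the assigned-odor test, since it matches the stated hypothesis.
3. Add, in the two 18 mg/ml arms, the between-arm test of strawberry vanilla>rose change and the between-arm test of tobacco>rose change. Add the difference of these two contrasts as a drift-free sensitivity analysis, with its estimate and interval.
4. State the interpretation in advance. A positive assigned-odor result is attributed to stronger conditioning only if the same-odor contrasts agree in direction, that is, if the strawberry vanilla contrast is positive and exceeds the tobacco contrast. Otherwise, report that odor-specific change cannot be excluded.
5. State the assumption that using one flavor does not alter the response to the other odor.

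Cost: a few extra group-level models on images already planned, with no new scanning. The combined contrast is imprecise: 2 to 3.6 times the variance and about 24% down to 18% power at 0.5 SD, for an assumed odor-change correlation of 0 to 0.8. Agreement in direction is therefore a modest safeguard, and lack of significance on that contrast should not be read as evidence against the hypothesis.

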7.2.4 Conditioning Phase Check-in Visit (Day 14 ± 7 days) - Remote

Participants will take part in a remote visit via Zoom to report their ECIG use and cigarettes per day (CPD) (collected in the daily logs). Participants will complete the measures outlined in Table 1. Participants will complete an adverse events assessment and discuss challenges to using their e-cig daily and study staff will assist in problem solving barriers to compliance. At the end of the visit participants will be instructed to remain abstinent from all tobacco products including their ECIG for 14 hours prior to the next study visit and to eat before their next study visit.

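### The exploratory aim sets a Day 0–28 BOLD change against a Day 14–28 craving change, although Table 1 schedules craving at Visit 2

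*Combined protocol and SAP*

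**What the plan says.** Section 8.3 defines the imaging change: "a difference z- statistic image will be calculated by subtracting the baseline image from the post-conditioning image". The scans are at Visit 2 (Day 0) and Visit 4 (Day 28 ± 7).

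The Exploratory Behavioral Aim in the same section looks for regions where BOLD change correlates with behavioral change. It takes satisfaction, "craving, and dependence collected at the 2-week check-in and post-randomization visit". For liking it uses a different pair of visits: "changes in ECIG liking collected at the baseline and post-randomization visits".

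Table 1 (section 7.2.5) marks Craving at Visits 2, 3 and 4. ECIG dependence and the ECIG evaluation scale are marked at Visits 3 and 4 only.

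On abstinence, section 7.2.2 instructs 14 hours without tobacco before Visit 2. Section 7.2.4 has participants told at Visit 3 to "remain abstinent from all tobacco products including their ECIG for 14 hours prior to the next study visit", which is Visit 4. No abstinence is instructed before Visit 3, the "Conditioning Phase Check-in Visit (Day 14 ± 7 days) - Remote". The instruction given at Visit 2 is to take at least 50 puffs per day (section 7.2.3).

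**The concern.** The aim asks whether change in odor cue-reactivity goes with change in craving. That is easiest to interpret when both changes cover the same period and are measured in the same state. As written, the imaging change spans the whole conditioning phase and the craving change spans its second half. Any shift in craving during the first two weeks on the assigned product is in the BOLD difference but not in the craving difference.

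For craving this is avoidable, because a Day 0 value is scheduled. A second possible mismatch is state. If craving at Visit 4 is rated after 14 hours of abstinence and craving at Visit 3 is not, the difference contains an acute abstinence response as well as change over time. A null or weak correlation would then be hard to read.

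**Working it through.** The plan states no sample size, power or alpha for this aim, so there is no figure to reproduce. The check compares visits and then gives an illustration.

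**Intervals**

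| Measure | Scheduled (Table 1) | Change used (section 8.3) | Nominal span |
|---|---|---|---|
| BOLD | Visits 2, 4 | Visit 2 to 4 | 28 days |
| Craving | Visits 2, 3, 4 | Visit 3 to 4 | 28 − 14 = 14 days |
| ECIG dependence | Visits 3, 4 | Visit 3 to 4 | 14 days, no earlier value |
| ECIG evaluation scale | Visits 3, 4 | Visit 3 to 4, if this supplies satisfaction | 14 days, no earlier value |

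The craving change covers 14/28 = 50% of the imaging interval. Starting at Visit 2 would make it 28/28.

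**State.** The imaging change runs between two visits that both carry the 14-hour instruction. The craving change starts at a visit without one.

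**Illustration of size (assumptions, not in the documents).** Write C0, C14 and C28 for craving at the three visits. Suppose BOLD change relates to craving only through the full change C28 − C0. The observed correlation is then the true one multiplied by k = corr(C28 − C0, C28 − C14).

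- Equal variances σ² and equal correlations ρ: the covariance is σ²(1 − ρ) and each variance is 2σ²(1 − ρ), so k = 0.50.
- Independent increments of equal variance v: k = v / √(2v · v) = 0.71.

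| True r | r × 0.71 | r × 0.50 |
|---|---|---|
| 0.30 | 0.21 | 0.15 |
| 0.40 | 0.28 | 0.20 |
| 0.50 | 0.35 | 0.25 |

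For a single correlation, two-sided 0.05, with all n = 56 randomized, approximate power is Φ(atanh(r)·√(n − 3) − 1.96):

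- r = 0.40: 0.424 × 7.28 − 1.96 = 1.12, giving 87%.
- r = 0.283: 0.291 × 7.28 − 1.96 = 0.16, giving 56%.
- r = 0.20: 0.203 × 7.28 − 1.96 = −0.48, giving 31%.

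These figures show direction only. The planned analysis searches across brain regions, and fewer than 56 participants may have two usable scans.

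**The case against.** **Which craving is meant.** In section 8.3 the e-cigarette qualifier stands before satisfaction and may govern craving too. Table 1 has one unspecified Craving row, placed among withdrawal and cigarette measures. If an e-cigarette craving item first given at Visit 3 is intended, the Visit 2 value is not its baseline. This stands as an ambiguity, but the plan names no such item, so the text needs correcting on either reading.

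**Abstinence.** A reader might infer that the planned craving change certainly contains an abstinence effect. The documents do not support that. Non-abstinence at Visit 3 is inferred from a missing instruction. Sections 7.2.3 and 7.2.5 also let some questionnaires be completed by Zoom within 3 days after the Visit 2 scan and within ± 3 days of the Visit 4 scan. The color coding of Table 1 that would show which ones is not legible here. Moreover, an abstinence shift equal in all participants would not change a correlation; only variation between participants would.

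**Size.** A reader might infer a definite loss of power. The multipliers are assumed, and the loss need not occur if the relevant BOLD change happens mainly in the second half.

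**Visit gap.** The ± 7-day windows alone suggest a Visit 3 to 4 gap of 0 days (21 − 21) to 28 days (35 − 7). That overstates it. The 14-hour instruction given at Visit 3 excludes zero, and section 7.3 places Visits 2 to 4 within four weeks, which caps the gap at about 28 − 7 = 21 days.

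**Importance.** The aim is exploratory, and for dependence and the evaluation scale the shorter interval is forced. Both points stand and limit the weight of this comment. Neither accounts for the craving interval.

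**Conclusion.** The interval mismatch for craving is explicit in section 8.3, and Table 1 makes it avoidable, provided that the Table 1 Craving row is the measure meant. The planned change covers 14 of 28 nominal days. The mismatch in abstinence state is a reasonable inference, conditional on when craving is completed. The fall from 0.40 to about 0.20–0.28 rests on an assumed correlation of 0.5 to 0.7 between half-period and full-period change, and on BOLD change relating to craving only through the full change.

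It would be wrong to extend the criticism to every behavioral measure in the aim, or to Aims 1 to 3, whose analyses do not use craving. This is a modest correction to one covariate in an exploratory analysis.

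**What to change.** In the Exploratory Behavioral Aim:

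1. Name the craving instrument.
2. If it is the Table 1 Craving measure, define the covariate as Visit 4 minus Visit 2, with both ratings taken at the scan session and not in the separate Zoom session.
3. Keep the Visit 3 to Visit 4 change only for measures with no Visit 2 value (ECIG dependence, ECIG evaluation scale), and state that it covers the second half of conditioning.
4. If an e-cigarette craving item first collected at Visit 3 is intended, name it and state the same limitation.

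Adding study-arm terms to the model is an optional, separate matter that this point does not require.

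The cost is a change of wording made before analysis, plus a line fixing when craving is rated. No visit or measure is added. If some craving ratings have already been collected by Zoom, record the session and report it as a limitation.
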